Electronic PHI will be stored on servers behind the VA firewall accessed by password-protected VA computers. Each subject is assigned a unique identifier (study ID) based on a study identifier and number (i.e., CCTA-xxx). Only coded or de-identified data, not PHI, are used for analysis. The file linking the study ID to the patient's name will be stored in a separate password-protected file on a secure server behind the VA firewall.

Coded data will be stored on OHSU's REDCap application, a highly secure and robust web-based research data collection and management system. No identifiable information will be entered into this application at any time. The statisticians will not have access to the code or PHI at any time. The spreadsheet linking the code to the subject will remain behind the VA firewall at VAPORHCS. Once the study has ended, the link will be stored by the VAPORHCS Research & Development Service.

Data will be collected and stored in a manner intended to preserve patient confidentiality. To preserve privacy, only approved study personnel will conduct study visits or access study records. All study visits will occur in private offices to preserve participants' privacy.

Certificate of Confidentiality

To further protect subject's privacy and confidentiality, the investigators will obtain a Certificate of Confidentiality from the National Institute of Health. With this Certificate, the investigators cannot be forced (for example by court subpoena) to disclose information that may identify subjects in any federal, state, or local civil, criminal, administrative, legislative, or other proceedings.

The informed consent document will include a statement that this study has a Certificate of Confidentiality and will describe the type of information that will be included in the subjects VHA medical record.

VA-SPECIFIC REQUIREMENTS:

N/A. The study does not include a Certificate of Confidentiality.

Information and/or Specimen Management

VA-SPECIFIC REQUIREMENTS:

All study data derived from subject procedures will be obtained specifically for research purposes. Data will be stored in a manner intended to preserve patient confidentiality. Raw data (e.g., collected from neuropsychiatric assessment visit procedures) will be stored in locked cabinets and on password protected computers in limited access folders behind the VA firewall. Each subject is assigned a unique identifier (study ID) based on a study identifier and number (i.e., CCTA-xxx). Only coded or de-identified data, not PHI, are used for analysis. Coded data will also be stored on OHSU's REDCap application, a highly secure and robust web-based research data collection and management system. The file linking the unique identifier with the patient's name will be stored in a separate password-protected file on a secure computer behind the VA firewall. Consent forms and the key linking names to identifiers will be stored in locked file cabinets or on password protected computers in limited access folders behind the VA firewall, and the key and consents will be stored

separately from the de-identified data files. Once the study has ended, the link will be stored by the VAPORHCS Research & Development Service.

Disclosure/Sharing:

VA-SPECIFIC REQUIREMENTS:

N/A. The study does not include disclosure/sharing outside the IRB-approved VAPORHCS study personnel.

Transfer of Data Ownership

VA-SPECIFIC REQUIREMENTS:

N/A. The study does not include transfer of data ownership.

Web Application(s), Mobile Device(s) and/or Mobile Application(s):

VA-SPECIFIC REQUIREMENTS:

N/A. The study does not include web application(s), mobile device(s) and/or mobile application(s).

A study team member will schedule study visits and CCT sessions with the Veteran and then send the Veteran a link for VVC through the Virtual Care Manager platform (no direct email contact between Veteran and study personnel will be initiated; all contact will be through the Virtual Care Manager or other VA-approved scheduling systems to ensure that no PHI is sent over email). VVC precautions for safety will be verified (i.e., veteran's physical address at time of appointment in case of emergency). No recordings will take place during study visits or CCT sessions.

VA REDCap will not be utilized for this study since VA REDCap is an intranet-only application that would require participants to have an active VA network account to be able to complete questionnaires within the application. Instead, OHSU's REDCap server will be utilized to store questionnaire data. Veterans will have the choice of either completing questionnaires online (through OHSU REDCap) or on paper. If the Veteran chooses to complete the questionnaires online, a link to the online questionnaires will be sent in the mail in their appointment confirmation letter. If the Veteran chooses to complete the questionnaires on paper, the paper questionnaires will be sent in the same envelope as their appointment confirmation letter. Only coded data will be stored on OHSU's REDCap application, a highly secure and robust web-based research data collection and management system. The questionnaires will have an alphanumeric code that will be linked to the participants' names in a separate spreadsheet that will remain behind the VA firewall at VAPORHCS. No identifiable information will be entered into REDCap at any time.

Data and Safety Monitoring Plan (DSMP)

See sponsor/3rd party protocol for requested information in this section. Indicate what heading/subheading in the 3rd party protocol that the information is located:

VA-SPECIFIC REQUIREMENTS:

[figure not shown]
Monitoring human participant recruitment, neuropsychiatric data collection, and data entry will be performed by the Co-PIs and study staff. Any adverse events will be reported immediately to the Co-PIs who will evaluate the patient and determine if any additional evaluation or treatment is needed. [name] will ensure that adverse events are properly reported to the IRB. The study staff will examine all cumulative adverse events quarterly to determine if there are any systematic problems. The balance of risk to benefit will be continuously monitored by the Co-PIs, and the study may be modified or terminated if risks begin to outweigh benefit.

Study staff is trained on the protocols to ensure that procedures are being conducted within the scope of the approved protocols. [name], (Co-PI), a licensed psychologist and neuropsychologist, supervises [name] (Co-PI) and other clinical research staff in the administration and scoring of neuropsychological tests and psychological measures. Recruitment and enrollment will be reviewed monthly in meetings with [name] and [name]. At these meetings, the research team will problem solve recruitment issues to ensure that projected enrollment numbers are obtained. [name] will check procedures (at least monthly) to verify that they are being conducted per the approved protocol, including the responsibilities and roles for gathering and monitoring data. The data are recorded by research staff as it is collected, and data accuracy is verified by double scoring, data entry, and visual verification.

Step-by-Step Guidance on Conducting the Study

See sponsor/3rd party protocol for requested information in this section. Indicate what heading/subheading in the 3rd party protocol that the information is located:

The study procedures and timeline are outlined in **Figure 2** below.

References & Literature Cited

See sponsor/3rd party protocol for requested information in this section. Indicate what heading/subheading in the 3rd party protocol that the information is located:
References

American Psychiatric Association. (2013). *Diagnostic and Statistical Manual of Mental Disorders* (5th ed.).
Boden, M., & Hoggatt, K. (2018). Substance use disorders among Veterans in a nationally representative sample: Prevalence and associated functioning and treatment utilization. *Journal of studies on alcohol and drugs*, 79(6), 853-861. <https://doi.org/https://doi-org.liboff.ohsu.edu/10.15288/isad.2018.79.853>

Connolly, S. L., Stolzmann, K. L., Heyworth, L., Weaver, K. R., Bauer, M. S., & Miller, C. J. (2021). Rapid Increase in Telemental Health Within the Department of Veterans Affairs During the COVID-19 Pandemic. *Telemed J E Health*, 27(4), 454-458. <https://doi.org/10.1089/tmj.2020.0233>

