Overview: We will enroll up to 30 Veterans and assess feasibility, acceptability, and preliminary efficacy of ME-CCT-A via telehealth. Veterans will receive ME-CCT-A via telehealth and undergo two study evaluations (baseline and 8 weeks) while also continuing with their usual medical, psychiatric, psychotherapeutic, and/or substance use treatment. Feasibility will be assessed by examining data on recruitment and retention rates, rate of completion of the intervention, and feasibility of testing procedures and data collection methods. Acceptability will be assessed through feedback surveys after study completion. We will assess the preliminary efficacy of ME-CCT-A on objective cognitive performance, daily functioning, subjective cognitive complaints, and psychiatric and substance use outcomes.

Intervention: Once at least 4 eligible Veterans have completed baseline visits, the 8-week group will begin via telehealth. The virtual group will be held through VA Video Connect or another VA-approved video meeting tool. Group sessions will last for 2 hours and consist of interactive didactic information and discussion and activities that introduce a variety of cognitive strategies and external aids. [name] (Co-PI) and/or another study staff member will run the CCT groups. Intervention materials will be mailed to participants prior to group start date. Attendance of each Veteran at each session will be noted. Individual make-up sessions will be offered to Veterans who miss a session, and attendance at make-ups will be recorded.

ME-CCT-A Treatment Manual: The structure of the intervention is determined by the ME-CCT-A treatment manual, which has been tailored to each cognitive domain commonly affected by SUDs (Huckans et al., 2018). Session materials correspond to compensatory cognitive training for difficulties with learning, memory, processing speed, executive functioning (multitasking abilities), verbal functioning, concentration, and attention.

Additionally, session content in the updated manual is tailored to address other symptoms related to SUDs that might be influencing cognitive functioning and incorporates motivational interviewing methods. Table 1 outlines the structure and content of the ME-CCT-A treatment manual and group sessions.

[figure not shown]

Table 1. ME-CCT-A Session Content

Session	Major Concepts	Examples of Strategies	Session Activities	Home Exercise

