1	Intro and SUD/cognitive functioning psychoeducation	Creating a "home" for important items	Day planner use	Finding a home for the day planner
2	Organization and prospective memory Part I	Time management	Scheduling and concrete goal setting	Practice using the calendar
3	Organization and prospective memory Part II	Daily and weekly planning sessions	Enter lists and activities into the calendar	Follow through with planning sessions
4	Attention and concentration	Paying attention during meetings and conversations	Practicing paying attention during conversations	Active listening once a day
5	Learning and memory	Internal and external memory strategies	Practice memory strategies	Practice using a strategy everyday
6	Problem-solving and cognitive flexibility	Evaluating costs and benefits to identify better choices	6-step problem-solving method	Practice problem-solving with 2 life goals
7	Planning and goal setting	Goal setting	Identify and re-evaluate priorities	Practice planning a goal
8	Skill integration and review	Review, practice, goals, and planning for the future	How to maintain skills and apply them to goals	Provided with additional SUD-related resources

Assessment Protocol: Veterans will complete the virtual assessment battery (see Table 2) at baseline (approximately 0-2 weeks prior to ME-CCT-A) and follow-up (approximately 0-2 weeks following ME-CCT-A completion). The battery consists of performance-based tests of objective cognition functioning and functional capacity and self-report measures of subjective cognitive complaints/functioning, substance use, engagement in targeted lifestyle practices associated with improved cognition, and engagement in protective activities/factors associated with reduced relapse. The Client Satisfaction Questionnaire (CSQ-8) and a series of structured, open-ended questions specific to the study intervention will be included at follow-up to assess Veterans' satisfaction with the virtual CCT intervention. Assessments will take approximately 2 hours.

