The cognitive domains were selected for assessment because previous research by our group has demonstrated that SUDs can be associated with significant impairments in attention, memory, and executive functions, and because ME-CCT-A includes cognitive strategy training that specifically targets each of those domains (Huckans et al., 2021; Huckans, Fuller, Wheaton, et al., 2015; Huckans, Fuller, Chalker, et al., 2015; Huckans et al., 2010; Storzbach et al., 2017). Measures were selected because of their sound psychometric properties and their ability to be conducted virtually. Each neuropsychological measure has more than one form, minimizing test-retest confounds at our two assessment visits. Assessment measures will be scored according to standardized test procedures. All assessments will be administered by [name] (Co-PI) or another approved study member and supervised by [name]. (Co-PI), who is a licensed, credentialed, and privileged VA neuropsychologist.

Measure	Construct Assessed
Objective Cognitive Functioning and Functional Capacity (Neuropsychological Tests)	
Wide Range Achievement Test 5 (WRAT5)	Reading ability, premorbid IQ estimate (baseline only)
Neuropsychological Assessment Battery (NAB) Attention Module subtest: Digit Span	Auditory attention capacity and working memory
NAB Attention Module subtest: Driving Scenes	Visual attention and working memory
NAB Memory Module subtest: List Learning	Verbal learning and memory
NAB Memory Module subtest: Shape Learning	Visual learning and memory
NAB Memory Module subtest: Medication Instructions	Verbal learning and memory relevant to everyday functioning
NAB Memory Module subtest: Name, Address, and Phone Number	Verbal learning and memory relevant to everyday functioning
NAB Executive Functions Module subtest: Judgment	Everyday problem-solving/executive function
NAB Executive Functions Module subtest: Categories	Mental flexibility and categorization
Delis-Kaplan Executive Function System (D-KEFS) Verbal Fluency	Language
Self-report Measures (Questionnaire Battery)	
Brief Addiction Monitor (BAM)	Substance use factors; Risk/protective factors
Prospective-Retrospective Memory Questionnaire (PRMQ)	Cognitive symptoms
Portland Cognitive Strategies Scale 2.0 (PCSS)	Compensatory cognitive strategy use
PROMIS-57 Profile v2.1	Physical, mental, and social health
PROMIS v2.0 Cognitive Function 8a	Subjective cognitive functioning

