Client Satisfaction Questionnaire (CSQ-8)	Satisfaction with the intervention (follow-up only)
Timeline Followback (TLFB)	Alcohol and cannabis consumption over a given time period
Alcohol Use Disorders Identification Test (AUDIT-C)	Alcohol use

ANALYTIC PLAN.

All data analyses will be conducted by study personnel with expertise in statistics, using Excel, SPSS, or other statistical software approved by the VA.

Phase 2, Aim 2 Feasibility and Acceptability: Descriptive statistics will characterize the feasibility of recruiting and retaining Veterans. Recruitment will be deemed feasible if we successfully screen for eligibility 50% of Veterans referred to the study and enroll 75% of screened Veterans who meet all study inclusion criteria. Retention will be deemed successful if we achieve 75% completion for post-treatment assessments. Chi-square tests of association and t-tests will compare demographic and clinical characteristics of successfully versus unsuccessfully recruited and retained Veterans to identify characteristics of Veterans who may require more intensive recruitment or retention efforts in a future trial. Acceptability will be assessed through surveys on treatment satisfaction (i.e., CSQ-8 with additional study-specific items) following group completion. Treatment will be deemed acceptable if $\geq 70\%$ of Veterans score ≥ 24 on the CSQ-8.

Phase 2, Aim 3 Preliminary Efficacy: Descriptive statistics and exploratory analyses will be used to assess the normality of the data and homogeneity of variance. Although our small sample size will limit our power to detect significant differences between pre- and post-treatment measures, we will

conduct preliminary analyses using t-tests to examine whether pre-post changes are in the expected directions. We will examine effect size (Cohen's d) and significance of our measures.

Study Population

See sponsor/3rd party protocol for requested information in this section. Indicate what heading/subheading in the 3rd party protocol that the information is located:

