The proposed study is conducted at a single site. We propose to enroll up to 30 Veterans in this pilot trial. Because our primary purposes are to examine feasibility and acceptability to Veterans with AUD, achieving adequate statistical power is not a primary concern of this pilot clinical trial. Results from this study with a sample size of up to 30, combined with comparisons to similar studies of CCT with other Veteran groups (e.g., those with mild TBI history), will provide adequate information on expected effect size to allow for estimations of statistical power for a future proposal of a larger pilot trial.

Inclusion criteria include: 1) Male and female Veterans (>18 years) who meet criteria for AUD in early remission (>1 month, <12 months remission) based on the DSM-5 (American Psychiatric Association, 2013); 2) Concern about a mild cognitive decline that has been identified by the Veteran or a knowledgeable informant (e.g., SUD treatment providers), and the Veteran wants treatment for their cognitive concerns; and 3) Access to internet and webcam.

Exclusion criteria include: 1) Intoxication or impaired capacity to understand study risks and benefits; 2) Major Neurocognitive Disorder, dementia, or neurodegenerative disorder (e.g., Alzheimer's Disease); and/or 3) Auditory or visual impairments that would prevent ability to participate in the cognitive rehabilitation group or benefit from compensatory strategies.

Eligibility will be established by electronic medical record review and will be confirmed by the Veteran during the initial phone call.

1. VA-SPECIFIC REQUIREMENT (inclusion of non-Veterans):

N/A. The study does not include non-Veterans.

See sponsor/3rd party protocol for requested information in this section. Indicate what heading/subheading in the 3rd party protocol that the information is located:

Subject Identification/Recruitment

See sponsor/3rd party protocol for requested information in this section. Indicate what heading/subheading in the 3rd party protocol that the information is located:

Recruitment, eligibility screening, consenting, study visits, and CCT groups will be conducted by approved clinical research staff. A Waiver of Authorization and Informed Consent Process for Screening/Recruitment Purposes will be obtained to facilitate subject identification and recruitment.

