4. The Corporate Data Warehouse (CDW) will be utilized to compile a list of potential participants. IRB-approved study staff will use this list to conduct medical chart reviews (i.e., CPRS) to identify Veterans who meet study criteria, do not meet exclusion criteria, are able to provide informed consent, can attend visits virtually, and may be interested in participating in the research. Veterans who are identified as eligible will be sent a letter from the Mental Health Clinical Director, a letter of introduction from the study team, the study flyer, and a form with the option to opt-in or opt-out to hearing more about the research either by calling study staff or returning the enclosed opt-in/opt-out form. A self-addressed, postage-paid return envelope will be included for the Veteran's convenience. The letter will also state that if study staff does not receive a response within two weeks, the Veteran may be contacted by phone to verify receipt of the letter and be given the option to be mailed a second letter (if not received). Only verification of Veteran's address will be obtained for those who did not receive a letter. Study staff will call all Veterans who indicate interest to provide more information about the study, answer any questions the Veteran may have, and, if applicable, schedule the initial baseline visit.

An appointment confirmation letter will be mailed to a participant after they have scheduled their initial visit. An appointment confirmation letter will also be sent prior to their follow-up visit. If a participant is enrolled in the study and not returning phone calls to schedule additional research visits, a no-show letter will be sent in the mail asking the participant to contact the research coordinator to discuss their interest in their continued involvement in the research study. If the research coordinator does not hear back from the participant within two weeks of sending the letter, the participant will be disenrolled from the research study.

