As part of the study, we will collect the following individually identifiable health information from each participant: information from their VA Health Records such as diagnoses, progress notes, medication, lab and radiology findings; specific information concerning alcohol and drug abuse and HIV status; demographic information such as name, race, gender, age, birthdate, address, phone number, and clinic visit dates; questionnaires and neuropsychological measures. This information is necessary for our research because we plan to use medical record information to confirm eligibility and clinical participation in CCT. We will use contact information to reach participants and for scheduling. We will use demographic information to describe our sample (i.e., sample characteristics) and to determine if they moderate study outcomes. Questionnaires and neuropsychological measures will help us determine if CCT is efficacious and address our study aims.

Collaborative Research

VA-SPECIFIC REQUIREMENTS:

N/A. The study does not include Collaborative Research.

This study is being reviewed by OHSU-VA joint IRB and utilizes OHSU's REDCap. All study procedures are conducted on VAPORHCS property by VA staff on VA time.

Resources Available

VA-SPECIFIC REQUIREMENT:

All research study visits are conducted through phone or video, but the Co-PIs' existing research spaces (Portland campus: [name]; [name]) may be utilized to conduct the remote research study visits. Study staff will utilize video-capable computers either in the Co-PI's personal office/research spaces or from secure locations in their own homes.

This project is a logical extension of [name] (Co-PI), [name] (Co-PI), and [name] (Co-I) existing research programs, which focus on the effects of SUDs and the development of novel treatments for cognitive impairment. Pilot data from this study will be used to submit future VA and NIH grants. Thus, it is reasonable that [name], [name], and [name] will be using a small portion of their own protected research time, research staff's time, and their research space on this pilot project so that they may obtain continued funding for their research programs.

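### Do the four-Veteran start rule and the two-week baseline window conflict in a way that leaves the 75% retention verdict open?

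*Combined protocol and SAP*

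**What the plan says.** The Intervention paragraph of Research Design and Methods sets the start condition: "Once at least 4 eligible Veterans have completed baseline visits, the 8-week group will begin via telehealth". The Assessment Protocol paragraph in the same section sets the timing of the first battery: "baseline (approximately 0-2 weeks prior to ME-CCT-A". The Overview plans two evaluations per Veteran and enrollment of up to 30.

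The Analytic Plan gives the pass mark: "Retention will be deemed successful if we achieve 75% completion for post-treatment assessments". It does not say out of whom. The sentence just before it sets the recruitment marks: screening 50% of referred Veterans and enrolling 75% of those screened who qualify.

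Study Population explains the weight of this criterion: "our primary purposes are to examine feasibility and acceptability to Veterans with AUD". On logistics, the web-application section says: "A study team member will schedule study visits and CCT sessions with the Veteran". Subject Identification/Recruitment expects some non-response after enrollment: "a no-show letter will be sent in the mail asking the participant to contact the research coordinator". Without a reply in two weeks, the participant is disenrolled. The study procedures and timeline are assigned to Figure 2, which is not legible in the text reviewed.

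**The concern.** The two timing rules look as if they could collide. A minimum of four completed baselines cannot be guaranteed inside a two-week window if Veterans arrive slowly, miss appointments or withdraw. A group would then start below four, or some baselines would fall outside the window, or some Veterans would have a baseline and no group. The legible text ranks none of these. Repeating the battery is not an obvious way out, since the plan relies on alternate forms for two visits: "Each neuropsychological measure has more than one form, minimizing test-retest confounds at our two assessment visits".

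The third outcome touches a primary purpose of the study. If a few Veterans complete baseline but never start, the same data can pass or fail the 75% mark depending on whether they are counted. Counting them also mixes failure to assemble a group with failure to keep Veterans in it, and a later trial would fix those two problems differently.

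**Working it through.** The plan derives neither the 75% mark nor the sample size, so there is no stated figure to reproduce. From the plan come the minimum of four, the window of about two weeks, the maximum of 30 and the 75% mark. Accrual rates, missed-visit rates and follow-up rates are not in the documents and are assumed below.

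**1. Could the rules collide if nobody planned the start date?** Four evenly spaced baselines fit in 14 days if the spacing is at most 14/3 = 4.67 days, which is 1.5 per week. With Poisson accrual at rate λ per week, the chance that the first four span two weeks or less is P(Poisson(2λ) ≥ 3):

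| λ per week | Chance | Mean age of oldest baseline at start, 3/λ |
|---|---|---|
| 0.5 | 8% | 6 weeks |
| 1 | 32% | 3 weeks |
| 1.5 | 58% | 2 weeks |
| 2 | 76% | 1.5 weeks |
| 3 | 94% | 1 week |

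Unplanned starts would therefore often overrun. But staff book both the visits and the sessions, so baselines can be grouped before a planned start.

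**2. Can a planned start still fall short?** Assume each booked baseline is missed with chance p, independently, and can be rebooked once inside the window. The effective miss chance is p². P(fewer than 4 complete) is then:

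| p | 4 booked | 5 booked |
|---|---|---|
| 10% | 3.9% | 0.1% |
| 20% | 15.1% | 1.5% |
| 30% | 31.4% | 6.7% |

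Booking five is already allowed, because four is a minimum. For the same reason, 30 Veterans need not leave a remainder: 5×4 + 2×5 = 30.

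**3. When would the retention verdict split?** With 30 baselines, 0.75 × 30 = 22.5, so 23 follow-ups are needed. Let s Veterans have a baseline but no group, and T = 30 − s. The verdict splits at counts c with c/T ≥ 0.75 and c/30 < 0.75:

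| s | T | c | c/T | c/30 |
|---|---|---|---|---|
| 1 | 29 | 22 | 75.9% | 73.3% |
| 2 | 28 | 21, 22 | 75.0%, 78.6% | 70.0%, 73.3% |
| 3 | 27 | 21, 22 | 77.8%, 81.5% | 70.0%, 73.3% |

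**4. How likely is a split, given that Veterans are stranded?** With c ~ Binomial(T, r), where r is the assumed follow-up among starters:

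| s | r = 75% | 80% | 85% | 90% |
|---|---|---|---|---|
| 1 | 17.0% | 14.7% | 7.5% | 1.5% |
| 2 | 33.6% | 31.8% | 18.7% | 5.0% |
| 3 | 31.3% | 36.5% | 28.3% | 11.2% |

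These figures take for granted that s Veterans are stranded and none is carried forward.

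**5. How likely is a split overall?** Suppose only the last group can strand anyone, because earlier shortfalls join the next group. Sum over s = 1 to 3 the chance that exactly s of the last group's bookings complete baseline (step 2) times the step 4 figure. For r from 75% to 85%:

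- Four booked: about 1%, 4-5% and 8-11% for p = 10%, 20% and 30%.
- Five booked: under 0.1%, about 0.5% and about 2%.

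If every short group is carried to a later one, s = 0 and the chance is zero.

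**The case for a change.** The strongest argument for a change is that feasibility is a primary purpose, the 75% mark is fixed in advance, and its denominator is not. A denominator chosen after the counts are known can be chosen to pass, and even one stranded Veteran is enough for 22 completers to give two answers. The plan also foresees disenrolling Veterans who stop responding, without saying whether they stay in the count. Settling this would take a sentence or two and no new data: session attendance is recorded, and the Protected Health Information section lists "and clinic visit dates" among the items collected.

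The arithmetic stands, and so does the missing denominator. The link to group formation is weaker. An early baseline does not change the number of completers; only a Veteran who never starts does that, and any loss between baseline and the first session has the same effect. The ambiguity therefore belongs to the retention sentence alone. That sentence follows directly on the screening and enrollment marks, so its plain reading is completion among enrolled Veterans. No legible text suggests restricting it to those who started a group.

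A rule requiring more than four bookings per start would add little. The minimum already permits it, and it could lengthen the wait before baseline, where losses would escape any denominator that begins at baseline.

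**Conclusion.** No change follows; this is missing detail of a kind that investigators fill sensibly. The two timing rules are compatible: one says when a group may begin, the other gives an approximate window, and staff control both calendars. Read together, the group waits for its fourth baseline and the window gives slightly, which leaves retention untouched and affects only exploratory pre-post estimates. Following either rule as written does not produce a wrong result.

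What remains is an unnamed denominator that the order of the Analytic Plan largely settles in favor of enrolled Veterans. It matters only if Veterans are stranded without a group and follow-ups fall at 21 or 22 of 30 (22 only, if one is stranded). Under the assumed missed-visit and follow-up rates, with only the last group at risk, that chance runs from under 0.1% to about 11%, and it is zero if Veterans are carried forward. Because attendance is recorded, anyone with a baseline and no group can be counted when the results are reported, and a reader could then work out both percentages. No legible text makes a later trial depend on passing the 75% mark.

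This rests on the ordinary meaning of an approximate window and on enrollment reaching 30. The illegible timeline figure might settle the sequence outright.
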